Our primary process-focused outcome for Aim 4 is **micro-decision making**. Through focus group interviews with key ICU Liberation Collaborative participants, we specifically aim to describe micro-decision making about ABCDEF bundle implementation and to determine how and to what extent patient preferences are ascertained and considered when implementing evidenced-based ICU pain, sedation, MV liberation, and early mobility practices.

Conceptual Framework. Our approach is guided by the Consolidated Framework for Implementation Research (CFIR),⁴⁴ which provides a comprehensive taxonomy of operationally defined constructs from multiple disciplines (e.g., psychology, sociology) that are likely to influence implementation of complex programs; 39 constructs are organized across 5 major domains that interact to influence implementation effectiveness.

Aim 1: Estimate the effects of patient-level characteristics on ABCDEF bundle adoption.

Design and Rationale. In Aim 1, we will use existing SCCM ICU Liberation Collaborative data to estimate the effects that various non-modifiable factors exhibited by ICU adults at admission (i.e., patient-level characteristics) have on ABCDEF bundle adoption. Previous surveys, qualitative investigations, and systematic reviews reported that certain patient-level characteristics (e.g., instability, patient weight/size) may impede bundle delivery, but these studies were limited in use of self-reported (vs. actual) rates of implementation.^{35,36,125,126,128} Findings from this aim will for the first time objectively distinguish which patient-level characteristics affect delivery of the overall bundle and its individual elements. Findings will have immediate relevance to patient care by aiding in the design of specific implementation strategies focused on overcoming patient-level barriers.

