Local staff who attended a training webinar and as-needed support from SCCM managers entered de-identified data into the collaborative database at their individual hospitals. Data were collected retrospectively during a 6-month baseline period (January 2015-June 2015) and prospectively during a 14-month implementation period (January 2016-March 2017). During the baseline (pre-Collaborative) period, staff from each site entered data on the first 5 consecutively admitted ICU patients each month (30 baseline patients per site). Throughout the implementation period, site staff collected data on the first 15 consecutively admitted patients per month. For each patient, daily data were collected for a maximum of seven ICU days (average of 3.3 ICU-days per patient) or until patients transferred out of the ICU, were designated non-ICU status, or died.

Measures. Patient-level variables include: age, sex, race, ethnicity, language, body mass index (BMI), admitting diagnosis, severity of illness, and preadmission residence and mobility status. The severity of illness scores collected in the Collaborative included the Acute Physiology and Chronic Health Evaluation (APACHE) II,¹³⁰ APACHE III,¹³¹ and APACHE IV¹³² referent to the patient's status at the time of ICU admission.

Data analysis. We will conduct similar analyses for each of the performance measures (performed vs. not performed), including complete, proportional, and each element performance. We will first use descriptive statistics to examine data distribution, check for outliers, and summarize patient characteristics. Bivariate tests (e.g., *t* test or Chi-square statistics) will be used to compare patient characteristics in the pre-Collaborative and Collaborative periods.

Using multilevel segmented logistic regression modeling for interrupted time series data, we can model the likelihood of bundle performance change over time, both before and during the periods of Collaborative implementation. **Figure 2** shows a hypothetical example. The basic form of the level-1 model (Figure x, solid black line) can be written as $\text{Logit}(Y_{ij}) = \beta_{0j} +$

Figure 2. Segmented logistic regression for ITS data-A hypothetical example

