Design and Rationale. We propose a qualitative dominant, mixed-methods companion study to the *Discover-ICU Study*. This work will be performed in Year 2 of the Discover ICU study. We will conduct focus group interviews with interprofessional teams from ten (5) high- and (5) low- bundle-performing ICUs. This is a modified, positive-negative deviance approach to exploit differences between high performing and low-performing units that will be used to identify the ethical challenges (e.g., conflicts, tradeoffs) experienced by clinicians in daily bedside decision making about bundle implementation. Focus groups will be composed of interprofessional members (e.g., physicians, nurses, physical therapists, respiratory therapists, pharmacists, occupational therapists, speech language pathologists) of the ICU liberation team from each unit.

Setting/Sample. We will conduct the focus group interviews remotely via Zoom videoconferencing “rooms” (Zoom Video Communications, Inc), a procedure used successfully for interviews with clinicians in our organization and by others.¹⁴⁷ A total of 50 – 80 interprofessional team members will participate (5-8 participants each for 10 selected ICUs). This sample represents nearly 15% of the ICU Liberation Collaborative and will provide a substantive body of narrative data sufficient to address the research questions.

The OSU biostatistician, **[name]**, will conduct purposive selection of five ICUs that are high- performing and five ICUs that are low- performing on SBTs based on analysis from the Discover ICU study dataset. Selection

will also consider maximum variability on performance of SATs, early mobility/exercise, hospital geographic location, hospital size, and annual number of ICU admissions. We are conducting maximum variation sampling because high performing environments may have different approaches, considerations, and challenges in micro-decisions about implementing SATs, SBTs and early mobility than low-performing units. This method will also produce the most representative sample to ensure credibility and transferability of findings. If selected ICUs refuse or are unable to participate, we will replace from the sampling pool. This method will also produce the most representative sample to ensure credibility and transferability of findings.

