ICU clinicians participating in focus group interviews will be full or part-time ICU physicians, nurses, respiratory therapists, occupational and physical therapists, pharmacists and speech language pathologists who are members of the ICU liberation team in selected ICUs. **Inclusion criteria:** clinicians must be in ICU practice for at least 1 year and at least 18 years of age. **Exclusion criteria:** unit managers and administrators will be excluded to avoid any feelings of intimidation or fear of retribution among group members. Women of child-bearing age or pregnant women will not be excluded from this study.

Study Procedures

Recruitment. **[name]**, our SCCM research partner, will contact prospective ICU interprofessional teams to invite their participation and ascertain interest and willingness to participate in the focus groups. Once interest in focus group participation is obtained from the ICU teams by SCCM staff, the Ohio State University (OSU) research team will contact the ICU team lead by email (or phone, if emails do not elicit a response) and schedule the Zoom meeting.¹⁴⁷ Electronic informed consent will be distributed by the OSU team and completed by all participants before beginning the focus group interview.

Data Collection. *Unit Organizational and Demographic Characteristics:* We will collect information from the Organizational Survey¹³⁵ data contained in the parent study database to describe the ten participating units. This dataset includes information on (1) hospital and ICU characteristics and utilization, (2) ICU staffing patterns, and (3) ICU rounding and ICU liberation bundle practices. We will describe the 10 units in the focus group sample on characteristics of the hospital (i.e., type, locale, teaching status, total number of beds, annual admissions) and ICU (i.e., type, training programs; number of ICU and step-down beds, open, semi-open, or closed unit, and number of ICU admissions). We will also describe ICU staffing patterns (ICU MD, advanced practice provider, RN, and additional ICU team member staffing, education, and certification data) and ICU rounding and ABCDEF bundle practices. We will collect the following characteristics from focus group participants: profession, critical care accreditation, highest education, years in critical care, age category, sex, race/ethnicity.

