
Potential Problems and Alternative Approaches and Benchmarks for Success

Potential limitations of Aims 1 and 2 include the possibility of missing data and the large number of data elements to be analyzed. Our team has intimate knowledge of the database and the key measures we are using. We have collapsed the data into relatively broad categories based on the constructs/domains of the CFIR and will continue to refine these measures using the experience of the entire team. Should we find key elements missing, our continued relationship with the Collaborative sites will allow us to explore additional methods of addressing these limitations. While we have a rigorous plan to adjust for patient case mix in deriving ICU-level risk-adjusted bundle adoption rates, there will admittedly be unmeasured confounders (e.g., patient or caregiver preference) that may bias the ICU-level estimate. However, it is reasonable to expect that such unmeasured confounders will be distributed evenly across ICUs. Finally, there may be concern regarding our ability to recruit the necessary participants to complete the work proposed in Aims 3 and 4. As demonstrated in the sample **letters of support**, Collaborative members remain tremendously excited and committed to furthering the important work of bundle adoption.

Potential Pitfalls foreseen for Aim 4 are due to selection of high and low performing units for focus group participation will be based on data collected in 2015-2017, therefore unit characteristics may have changed and unit adherence may have improved or regressed since the data were collected. We also recognize that ICU environments and experiences in the care of mechanically ventilated patients are rapidly changing in response

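### Aim 4 contrasts ICUs labelled high or low on 2015-2017 data but does not record whether participants worked in the unit at that time

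*Combined protocol and SAP*

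**What the plan says.** All places are in the combined protocol and SAP.

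- **Unit selection (Aim 4, Setting/Sample).** Five high and five low performers on SBTs are chosen from the study dataset, with 5-8 participants in each.
- **Age of the label.** Under Aim 1, Procedures and Data Sources, the later data were collected "prospectively during a 14-month implementation period (January 2016-March 2017". The section on potential problems concedes that selection for "focus group participation will be based on data collected in 2015-2017, therefore unit characteristics may have changed", and that adherence may have moved either way.
- **Who may take part (Aim 4, Setting/Sample).** Participants are ICU clinicians "who are members of the ICU liberation team in selected ICUs". The design paragraph says that groups are made up of members "of the ICU liberation team from each unit". The experience rule is "clinicians must be in ICU practice for at least 1 year and at least 18 years of age".
- **What is recorded about them (Aim 4, Data Collection).** The list is "profession, critical care accreditation, highest education, years in critical care, age category, sex, race/ethnicity".
- **How the informants are described (Approach).** Aim 4 proceeds "Through focus group interviews with key ICU Liberation Collaborative participants".
- **How the label is used (Aim 4, Data Management and Analysis).** Themes are compared between high- and low-performing units in matrices, and also crossed with Organizational Survey data taken from the parent database.

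**The concern.** The high/low split is the backbone of Aim 4. It is meant to show how decision making differs between units that did well and units that did poorly. The label was earned by whoever staffed the unit up to March 2017, while the accounts come from whoever is on the liberation team at interview. Nothing in the eligibility rules connects the two groups. By contrast, Aim 3 (Setting and Sample) says that its informants will have worked in a Collaborative unit.

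If many speakers joined later, a theme could be read as explaining a unit's past performance although its source had no part in that performance. A real difference could equally be blurred. Neither could be seen in the data, because time in the unit is not among the recorded items.

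**Working it through.** **1. The plan's own figures.** 10 ICUs x 5 = 50 and 10 x 8 = 80 participants, as stated. 10/68 = 14.7%, which agrees with the stated share of nearly 15% of the Collaborative. That share counts ICUs, not people.

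**2. Who qualifies.** Taken together, the rules require (a) current membership of the selected ICU's liberation team and (b) one year of ICU practice. Condition (a) ties the person to the unit now. Condition (b) names no unit. Neither refers to 2015-2017 or asks for personal involvement in the Collaborative.

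**3. The time gap.** The timeline is given in study years and quarters without calendar dates. The text refers to the COVID-19 pandemic and cites 2020 publications, so I assume interviews between April 2020 and January 2022.

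- March 2017 to April 2020: 3 x 12 + 1 = 37 months.
- March 2017 to January 2022: 5 x 12 - 2 = 58 months.
- A participant with exactly 12 months of ICU practice would have started 37 - 12 = 25 to 58 - 12 = 46 months after the label data closed.

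Under these dates the criterion admits later arrivals and, taken literally, a whole group of them.

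**4. How many that could be.** No turnover figure is given, so this is an illustration. With a constant team size and yearly turnover t, the share that joined within the last y years is 1 - (1 - t)^y.

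| Assumed t | y | Share joined after March 2017 | In a group of 5 to 8 |
|---|---|---|---|
| 5% | 3 | 1 - 0.95^3 = 0.143 | 0.7 to 1.1 |
| 15% | 4 | 1 - 0.85^4 = 0.478 | 2.4 to 3.8 |
| 20% | 5 | 1 - 0.80^5 = 0.672 | 3.4 to 5.4 |

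The range runs from one person or fewer to most of the group, so the documents cannot settle the size.

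**5. What the recorded items can show.** Someone whose years in critical care fall short of the time since March 2017 must have arrived later. Someone with more years may have been in this unit throughout or may have moved from another ICU last year. The item therefore gives at best a lower bound on later arrivals.

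**6. Whether a stricter experience rule would help.** Requiring the one year to be in the selected ICU would still admit anyone who started there 25 to 46 months after the label data closed, by the arithmetic in step 3. It does not reach the labelled period.

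**The case against.** **Participants do belong to the unit.** A reader might infer from the experience rule alone that the contrast could rest on people who never worked in the labelled ICU. The documents do not support that. The sentence before the rule limits participants to the liberation team of a selected ICU, and the interview guide in Appendix A asks about a patient cared for on the group's own unit. What remains is that they may not have worked there during the labelled period.

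**The label's age is disclosed.** This is true and it lowers the weight of the point. The disclosure concerns unit characteristics and adherence. It does not mention staff turnover and leads to no data item or analysis.

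**Current staff are the right informants.** Groups are asked for a recent case and the research questions concern present decisions. This objection stands, and it also limits the remedy: a clinician present in 2016 describes present practice too, so a tenure flag cannot turn an account into evidence about 2016.

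**There is no conflict over who the informants are.** One could read the description of informants in Approach as a promise that the rules break. That is only arguable. Under Aim 1, Procedures and Data Sources, the same term is used for sites that obtained ethics approval, and the nearly-15% figure counts ICUs. On that reading, current teams of Collaborative ICUs satisfy the description.

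**The problem can be partly seen already.** Years in critical care identifies some later arrivals, and interview probes may change between groups. Both help, but neither recovers time in the unit systematically.

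**Conclusion.** The point holds as a minor one. Units carry a label from data ending in March 2017, participants may have joined the unit since, and the plan does not record the one fact that would show how many did. The gap of roughly 37 to 58 months rests on assumed interview dates. The 14% to 67% range rests on assumed turnover, and liberation-team members need not turn over like other staff. The documents establish neither that many participants will be later arrivals nor that the contrast will mislead. They establish only that the team could not tell. Aim 4 is qualitative-dominant and purposively sampled with no hypothesis test, so what is at stake is how themes are attributed, not an error rate.

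**What to change.** 1. Add two items to the Aim 4 participant form: start date in this ICU, and whether the person worked there in January 2016-March 2017 (yes/no).
2. Report the share present in that period for each unit, and carry the flag as a column in the high-versus-low matrices.
3. For each high-versus-low theme, check whether it also appears among participants who were present. Where it does not, or where few or none were present, report it as current practice in a unit that was high- or low-performing in 2015-2017, not as an explanation of that performance.
4. In the section on potential problems, name staff turnover as a further limit and say that the flag does not remove the age of the label.
5. In Approach, state whether Collaborative participants means individuals or sites.

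The experience rule need not change, since one year in this ICU would not reach the labelled period. No minimum number of long-tenured participants per group is proposed, because the documents give no basis for one. The cost is two form items, one matrix column and a few sentences. The items should be in place before the first group, because tenure is easiest to collect at interview.

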APPENDIX A. Focus Group Interview Guide

We are going to begin by asking you to think about a patient you recently cared for on your unit who required mechanical ventilation. We are specifically interested in learning about the decisions you and your team made regarding SATs, SBTs, and early mobility.

Please focus on whether or not you were able to actually conduct an awakening trial, a spontaneous breathing trial and mobility. What were some of the factors you all considered in implementing spontaneous awakening trials, spontaneous breathing trials, and early mobility/ exercise with this patient?

Take a few minutes as a group to write down perhaps in bullet points or full sentences, if you like, the de-identified (no names) story of a single day in caring for the patient. It doesn't have to be a perfect case – just one that is typical or that you'd really like to talk about.

[allow 10 minutes for group discussion]

Select a member to begin telling the story. Others are encouraged to add.

Tell me about the considerations you had and decisions that you made regarding SAT for this patient?

- What conflicts did you encounter?
- What tradeoffs did you make or think about?

Tell me the considerations you had and decisions that you made regarding SBT for this patient?

- What conflicts did you encounter?
- What tradeoffs did you make or think about?

Tell me the considerations you had and decisions that you made regarding early mobility for this patient?

- What conflicts did you encounter?
- What tradeoffs did you make or think about?

Can you describe interactions with the patient about the SAT, SBT, and early mobility procedures?

- How did you inform the patient?
- What methods of communication are used with MV patients during bundle implementation?
- Is this the same or different for other interactions in the care of patients in your unit?

What input did the patient have in the process?

- How would you describe the patient's preferences about A, B, and E bundle procedures?
- How did the patient respond?
- In what ways did you use the patient's preferences and responses in decisions about beginning, continuing or stopping the A, B, or E bundle procedures?
 - **How did you weigh the patient's responses in A, B, and E?**

How does this patient compare with other typical patients on your unit? (ascertain if this is an extreme case) [probe for a typical or contrasting case]

